HIPAA	Health Insurance Portability and Accountability Act		
ICD	Informed Consent Document		
	International Council for Harmonization of Technical Requirements for		
ICH	Pharmaceuticals for Human Use		
IRB	Institutional Review Board		
PPE	Personal Protective Equipment		
qPCR	Quantitative Polymerase Chain Reaction		
SAE	Serious Adverse Events		
SCH	Stratum Corneum Hydration		
TEWL	Transepidermal Water Loss		

EpiCeram for skin protection in healthcare workers using personal protective equipment.

Synopsis

Protocol #: PPE-01

Background

During the current COVID-19 pandemic, health care workers (HCW) report that the prolonged use of personal protective equipment (PPE), particularly gloves and face covering, results in irritant contact dermatitis manifested by symptoms of pain, itching, burning and non-specific discomfort of the hands and face and associated visible physical changes of erythema, dryness, roughening and cracking of the affected skin (Jiang, et al 2020). These changes are aggravated by frequent hand washing and antimicrobial alcohol use. These irritative changes are likely associated with defects in the normal barrier structure and function of the skin, including, but not limited to, lowering of surface pH, excessive water loss, alteration of skin microbiome, lowered resistance to penetration by allergens and pathogens and immunological dysfunction. It is unknown whether these changes could increase the likelihood of S. aureus skin contamination or, in people exposed to, but not systemically ill with, COVID-19 to act as "silent" carriers of coronavirus.

EpiCeram, a three, lipid emollient, has been shown to improve barrier structure and function, reduce skin pH, helps restore the microbiome toward normal, improve immunological function and reduce symptoms associated with disrupted skin surfaces (Elias 2014, Elias 2019 and Kircik 2014). In contrast, some readily available over the counter skin care products may actually increase barrier dysfunction and aggravate skin disease (Li 2017, Elias 2019).

Study Objectives

- 1. To evaluate the ability of EpiCeram to reduce signs and symptoms of skin irritation in HCW using PPE on the face and hands.
- 2. To evaluate the ability of EpiCeram to improve measurements of skin barrier function during continued use of PPE on the face and hands.
- 3. To evaluate the ability of EpiCeram to reduce skin surface S. aureus load.

Study design

This will be a one (1) month, open label study. Subjects must be HCW who have used face and hand PPE at least four (4) days a week for a minimum of one (1) month (or, depending on shift work, at least 24 hours/week) and who have new (after March 1, 2020) symptomatic skin irritation on the hands and/or face. No change to required hand washing protocols or other protective measures will be required.

At Visit 1 (Screening) the study will be explained, and an informed consent document (ICD) signed. Subjects will be entered into the electronic data capture (EDC) system using a direct data capture (DDC) tablet. Subjects will complete an overall skin irritation assessment on 0-10 scale where 0 = none and 10 = worst. If it is equal to or greater than 4, the subject may proceed to enrollment provided all other inclusion and exclusion are met.

If the subject has not used any lotions and emollients for the previous one (1) week on the face and hands, washout is not necessary, and Baseline visit activities may be performed at the Screening visit. Subjects requiring washout, will refrain from using any lotions and emollients for one (1) week between Visits 1 and 2 and then, for the duration of the study. Visit 2 (Baseline) will occur seven (7) days after Visit 1.

At Visit 2, subjects will complete an overall skin irritation assessment on a 0-10 scale where 0 = none and 10 = worst. Subjects will complete skin symptom scales of pain, redness, dryness, roughness, itching and cracking on a scale on a 0-10 scale where 0 = none and 10 = worst. A manual describing detailed steps for collection of laboratory, photographic and skin surface measurements will be provided to the site by the sponsor. Vendors will supply training and references for the camera and EDC system.

Photographs: Digital 3D photographs will be taken of the face and back of the hand. The face photo will be a two (2) inch by three (3) inch area of the cheek without identifying features. The hand photo will be the worst area of involvement as selected by the subject. Skin Function Testing: Measurements of transepidermal water loss (TEWL) with stratum

corneum hydration (SCH) and surface skin pH will be taken on the web between the 3rd and 4th metacarpophalangeal (MCP) joints on the dorsum of the dominant hand used.

Laboratory Testing: Two types of specimens will be obtained; a swab and tape stripping. A single skin swab for bacterial qPCR will be obtained from the palm of the dominant hand. Non-invasive tape stripping of surface cells (3 strips/sample) will be performed at 2 sites; on the web between the 3rd and 4th metacarpophalangeal (MCP) joints on the dorsum of the dominant hand for antimicrobial peptides (AMP) and three (3) strips/sample from the web between the 2nd and 3rd MCP joints on the dominant hand for free fatty acids. See the manual for detailed instructions on specimen collection. The subject will then be directed to apply EpiCeram to the hands (wrist to fingertips, back and front) and face at least three (3) times daily (about every 8-10 hours), more often if the subject wishes.

At Visit 3 (Final), 28 days later subjects will complete an overall skin irritation assessment on a 0-10 scale where 0 = none and 10 = worst. Subjects will complete skin symptom scales of pain, redness, dryness, roughness, itching and cracking on a scale on a 0-10 scale where 0 = none and 10 = worst. Photos, skin function, swab and tape stripping will be in the same location as Visit 2. Photographs: Digital 3D photographs will be taken of the face and back of the hand. The face photo will be a two (2) inch by three (3) inch area of the cheek without identifying features. The hand photo will be the worst area of involvement as selected by the subject.

Skin Function Testing: Measurements of transepidermal water loss (TEWL) with stratum corneum hydration (SCH) and surface skin pH will be taken on the dominant hand on the dorsum of the 3rd and 4th metacarpal phalanges.

Laboratory Testing: Two types of specimens will be obtained; a swab and tape stripping. A single skin swab for bacterial qPCR will be obtained from the palm of the dominant hand. Non-invasive tape stripping of surface cells (3 strips/sample) will be performed at 2 sites; on the web between the 3rd and 4th metacarpophalangeal (MCP) joints on the dorsum of the dominant hand for antimicrobial peptides (AMP) and three (3) strips/sample from the web between the 2nd and 3rd MCP joints on the dominant hand for lipids. The subject will then be directed to apply EpiCeram to the hands and face at least three (3) times daily (about every 8-10 hours), more often if the subject wishes.

Primary Endpoint

- 1. Change in patient reported outcome of face and hand skin symptoms from baseline to Day 28, of at least 2 points on a 0-10 point scale where 0 = none and 10 = worst.
 - a. pain
 - b. redness
 - c. dryness
 - d. cracking
 - e. roughness
 - f. itching
 - g. overall skin irritation

Secondary endpoints

- 1. Change from baseline to Day 28 in pH.
- 2. Change from baseline to Day 28 in TEWL.
- 3. Change in S. aureus colonization from baseline to Day 28.

Inclusion Criteria

- 1. HCW using PPE at least 6 hours/day, 4 days/week or, depending on shift work, 24 hours/week, for at least one (1) month,
- 2. Men or women, any age
- 3. Overall skin irritation score of at least 4 on 0-10 scale where 0 =none and 10 =worst
- 4. Must be willing to stop use of any other emollient and lotion for one (1) week between screening and baseline visit and for the duration of the study.
- 5. Participant is willing to stop use of, or not begin, use of any topical corticosteroids, emollients and lotions to the hands and face for the duration of the trial.

Exclusion Criteria

- 1. History of any skin disorder existing prior to March 1, 2020 characterized by chronic visible lesions or skin irritation symptoms including, but not limited to atopic dermatitis, eczema, moderate-severe acne, chronic dry skin and psoriasis.
- 2. Use of topical or systemic corticosteroids within one (1) month of baseline visit.
- 3. History of any significant medical condition that, in the opinion of the investigator, might put the subject at risk in this trial.
- 4. Participation in another clinical trial within 30 days or 5 half-lives of the study agent, whichever is longer.

Study test item

EpiCeram® 90 gram tubes

Number Subjects

Fifty (50) subjects will be evaluated in this study. Accordingly, 55 subjects will be enrolled to allow for a 10% drop out rate.

Efficacy Measurements

- 1. Symptom scales
 - a. pain
 - b. redness
 - c. dryness
 - d. cracking
 - e. roughness
 - f. itching
 - g. overall skin irritation
- 2. Surface Skin pH
- 3. TEWL
- 4. SCH
- 5. Antimicrobial peptides (LL-37, HBD-2)
- 6. Free fatty acids
- 7. Bacterial qPCR
 - a. S. aureus
 - b. MRSA
 - c. S. epidermidis

Safety Measurements

Adverse Events

Statistics

Descriptive statistics will be calculated for all demographic and clinical characteristics at baseline and study outcomes for each time period. Means and standard deviations will be presented for continuous variables (e.g., age) and proportions and frequencies for categorical

variables (e.g., sex). Paired t-tests will be used to assess unadjusted differences in primary outcomes of face and hand skin irritation symptoms (pain, redness, dryness, cracking, roughness, itching and overall skin irritation) and secondary outcomes of pH, TEWL, and S. aureus colonization level between the baseline visit and Day 28 follow-up visit. Analysis will be performed on the Intention-to-Treat (ITT) sample. Standard data quality checks will be performed. The sample size of n = 50 is sufficiently powered $(1 - \beta = 0.80)$ to identify a medium effect size of d = 0.4 in a two-tailed test with α set at 0.05. Given the multiple primary endpoints, *p*-values will be reported with high precision (four percentage points) to allow for multiple comparisons adjustments as desired.

EpiCeram for skin protection in healthcare workers using personal protective equipment.

Protocol #: PPE-01

1. Introduction:

During the current COVID-19 pandemic, health care workers (HCW) report that the prolonged use of personal protective equipment (PPE), particularly gloves and face covering, results in irritant contact dermatitis manifested by symptoms of pain, itching, burning and non-specific discomfort of the hands and face and associated visible physical changes of erythema, dryness, roughening and cracking of the affected skin (Jiang, et al 2020). These changes are aggravated by frequent hand washing and antimicrobial alcohol use. These irritative changes are likely associated with defects in the normal barrier structure and function of the skin, including, but not limited to, lowering of pH, excessive water loss, alteration of skin microbiome, lowered resistance to allergens and pathogens and immunological dysfunction. It is unknown whether these changes could increase the likelihood of S. aureus skin contamination or, in people exposed to, but not systemically ill with, COVID-19 to act as "silent" carriers of coronavirus.

EpiCeram, a marketed product, is a three lipid emollient that has been shown to improve barrier structure and function, reduce skin pH, helps restore the microbiome components toward normal, improve immunological function and reduce symptoms associated with disrupted skin surfaces (Elias 2014, Elias 2019 and Kircik 2014). In contrast, some readily available over the counter skin care products may actually increase barrier dysfunction and aggravate skin disease (Li 2017, Elias 2019).

2. Hypotheses

- a. The signs and symptoms of skin irritation secondary to extensive use of PPE will be accompanied by measurable defects in skin barrier structure and function.
- b. EpiCeram will improve measurements of skin barrier integrity.
- c. Signs and symptoms of skin irritation will improve after one month of EpiCeram use.
- d. Improvement of skin barrier function will restore reduce skin colonization by pathogenic bacteria.

3. Study design

This will be a one (1) month, open label study. Subjects must be HCW who have used face and hand PPE at least four (4) days a week for a minimum of one (1) month (or, depending on shift work, at least 24 hours/week) and who have new (after March 1, 2020) symptomatic skin irritation on the hands and/or face. No change to required hand washing protocols or other protective measures will be required.

At Visit 1, Screening the study will be explained and an informed consent document (ICD) signed. Subjects will be entered into the electronic data capture (EDC) system using a direct data capture (DDC) tablet. Subjects will complete an overall skin irritation assessment on 0-10 scale where 0 = none and 10 = worst. If it is equal to or greater than 4, the subject may proceed to

enrollment provided all other inclusion and exclusion are met. If the subject has not used any lotions and emollients for the previous one (1) week on the face and hands, washout is not necessary, and Baseline visit activities may be performed at the Screening visit. Subjects requiring washout, will refrain from using any lotions and emollients for one (1) week between Visits 1 and 2 and then, for the duration of the study. Visit 2 (Baseline) will occur seven (7) days after Visit 1.

At Visit 2, subjects will complete an overall skin irritation assessment on a 0-10 scale where 0 = none and 10 = worst. Subjects will complete skin symptom scales of pain, redness, dryness, roughness, itching and cracking on a scale on a 0-10 scale where 0 = none and 10 = worst. A manual describing detailed steps for collection of laboratory, photographic and skin surface measurements will be provided to the site by the sponsor. Vendors will supply training and references for the camera and EDC system.

Photographs: Digital 3D photographs will be taken of the face and back of the hand. The face photo will be a two (2) inch by three (3) inch area of the cheek without identifying features. The hand photo will be the worst area of involvement as selected by the subject.

Skin Function Testing: Measurements of transepidermal water loss (TEWL) with stratum corneum hydration (SCH) and surface skin pH will be taken on the web between the 3rd and 4th metacarpophalangeal (MCP) joints on the dorsum of the dominant hand used.

Laboratory Testing: Two types of specimens will be obtained; a swab and tape stripping. A single skin swab for bacterial qPCR will be obtained from the palm of the dominant hand. Non-invasive tape stripping of surface cells (3 strips/sample) will be performed at 2 sites; on the web between the 3rd and 4th metacarpophalangeal (MCP) joints on the dorsum of the dominant hand for antimicrobial peptides (AMP) and three (3) strips/sample from the web between the 2nd and 3rd MCP joints on the dominant hand for free fatty acids. See the manual for detailed instructions on specimen collection. The subject will then be directed to apply EpiCeram to the hands (wrist to fingertips, back and front) and face at least three (3) times daily (about every 8-10 hours), more often if the subject wishes.

At Visit 3 (Final), 28 days later subjects will complete an overall skin irritation assessment on a 0-10 scale where 0 = none and 10 = worst. Subjects will complete skin symptom scales of pain, redness, dryness, roughness, itching and cracking on a scale on a 0-10 scale where 0 = none and 10 = worst. Photos, skin function and laboratory testing will be in the same location as Visit 2. Photographs: Digital 3D photographs will be taken of the face and back of the hand. The face photo will be a two (2) inch by three (3) inch area of the cheek without identifying features. The hand photo will be the worst area of involvement as selected by the subject.

Skin Function Testing: Measurements of transepidermal water loss (TEWL) with stratum corneum hydration (SCH) and surface skin pH will be taken on the dominant hand on the dorsum of the 3rd and 4th metacarpal phalanges.

Laboratory Testing: Two types of specimens will be obtained; a swab and tape stripping. A single skin swab for bacterial qPCR will be obtained from the palm of the dominant hand. Non-invasive tape stripping of surface cells (3 strips/sample) will be performed at 2 sites; on the web between the 3rd and 4th metacarpophalangeal (MCP) joints on the dorsum of the dominant hand

for antimicrobial peptides (AMP) and three (3) strips/sample from the web between the 2^{nd} and 3^{rd} MCP joints on the dominant hand for free fatty acids. See the manual for detailed instructions on specimen collection. The subject will then be directed to apply EpiCeram to the hands (wrist to fingertips, front and back) and face at least three (3) times daily (about every 8-10 hours), more often if the subject wishes. The investigator will assess the subject' Response to Therapy on a scale of 1-5 with 1 = no response and 5 = best response. Subjects may then be discharged from the study.

4. Primary endpoints

- a. Change in patient reported outcome of overall face and hand skin irritation symptoms from baseline to Day 28, of at least 2 points on a 0-10 point scale where 0 = none and 10 = worst.
- b. Change in any two of the following specific skin irritation symptoms of at least 2 points on a 0-10 point scale where 0 = none and 10 = worst.
 - 1. pain
 - 2. redness
 - 3. dryness
 - 4. cracking
 - 5. roughness
 - 6. itchiness
 - 7. overall skin irritation

5. Secondary endpoints

- a. Reduction from baseline to Day 28 in pH
- b. Reduction from baseline to Day 28 in TEWL
- c. Reduction in S. aureus colonization from baseline to Day 28

6. Subject Selection Criteria

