6.2 Exclusion Criteria

a. History of any skin disorder existing prior to March 1, 2020 characterized by chronic visible lesions or skin irritation symptoms including, but not limited to

atopic dermatitis, eczema, moderate-severe acne, chronic dry skin and psoriasis.

- b. Use of topical corticosteroids within one (1) month of baseline visit.
- c. History of any significant medical condition that, in the opinion of the investigator, might put the subject at risk in this trial.
- d. Participation in another clinical trial within 30 days or 5 half-lives of the study agent, whichever is longer.

7. Test Item and Proscribed Treatments

This is an open label study. All subjects will receive EpiCeram, delivered in 90 gm tubes. The EpiCeram cream will be applied to face and hands at least three (3) times per day, about every 8 hours taking care to apply after bathing and before applying any makeup. Subjects are prohibited from using any other skin lotion by prescription or over the counter. Subjects are specifically prohibited from using any corticosteroid containing skin products.

8. Number of Subjects

Fifty (50) subjects will be evaluated in this study. To account for subjects who fail to complete the trial fifty-five (55) subject will be enrolled.

9. Safety measurements Adverse events

10. Efficacy measurements

- a. Symptom scales
- b. TEWL
- c. Hydration
- d. Skin pH
- e. Skin surface bacterial qPCR

11. Study Procedures

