11.1 Screening visit

At least one (1) week prior to the baseline visit patients will be evaluated for inclusion in the study. Patients will have the study thoroughly explained to them and all their questions will be answered. Patients will sign the Informed Consent Document (ICD) before any study related procedures are performed. By definition, a patient becomes a study subject once he/she has signed the informed consent document. Every patient must have the opportunity to take home an unsigned copy of the ICD to discuss the study with family or friends and consider their decision whether to participate.

Screening and Baseline procedures may occur on the same day the study is first presented if the patient elects to proceed at that time and meets the inclusion and exclusion criteria including the washout requirement. A manual describing detailed steps for collection of laboratory, photographic and skin surface measurements will be provided to the site by the sponsor. At the Screening visit, each subject will be entered into the EDC system using a DDC tablet which will issue a unique identifier.

Subjects who agree to participate will perform the following:

- a. Review and sign the Informed Consent Document including consent for photos.
- b. Assess for overall irritation score of ≥ 4 on the previously described scale of 0-10.
- c. Assess for meeting all inclusion and exclusion criteria.
- d. The subject will be instructed to stop using (washout) emollients and lotions currently in use on the hands and face for one (1) week and for the duration of the study.
- e. The subject will be instructed to return in one (1) week for the Baseline visit. If washout requirement is met, Baseline visit activities may be performed at the Screening visit. Instruct subjects to refrain from washing hands and face for 2-hours prior to each visit.

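### Secondary TEWL and pH endpoints: the protocol text neither sets nor records time since the last EpiCeram application at Day 28, and it conflicts on whether hand or face is measured

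*Combined protocol and SAP*

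**What the plan says.** **Endpoint and test.** Section 5 lists "Reduction from baseline to Day 28 in TEWL" and a matching item for pH. It names no body site and no condition on product use before the reading. Section 21 applies the paired t-test planned for the primary outcomes to pH and TEWL, and it also names no site.

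**Product state at the two visits.** For baseline, Section 3 says "Subjects requiring washout, will refrain from using any lotions and emollients for one (1) week between Visits 1 and 2"; subjects already a week free of such products skip this step. From Visit 2 the Section 3 instruction is to apply EpiCeram "at least three (3) times daily (about every 8-10 hours), more often if the subject wishes". Section 7 words the interval differently: "about every 8 hours taking care to apply after bathing and before applying any makeup". Section 11.2 adds that application is at home, to clean skin. Section 14.11 says the product has at least two occlusive ingredients.

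**Pre-visit rule.** Section 11.1 says "Instruct subjects to refrain from washing hands and face for 2-hours prior to each visit", and the Appendix II footnote repeats it for Baseline and Day 28. Application is not mentioned.

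**Manual.** Section 3 states: "A manual describing detailed steps for collection of laboratory, photographic and skin surface measurements will be provided to the site by the sponsor". It is not among the documents supplied.

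**Site.** The synopsis and Section 3 place TEWL, stratum corneum hydration (SCH) and pH on the dominant hand. Sections 11.2 and 11.3 ask for pH on face and hand and give no site for TEWL. Appendix II lists face and hand for all three.

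**The concern.** The washout controls what is on the skin at baseline; the visible text has no counterpart at Day 28. Section 5 scores a reduction, so if product on the skin lowers the TEWL reading, that lowering counts towards the endpoint. With no control arm and no recorded application time, the analysis could neither separate this from a change in the skin nor describe how far readings differed in time since application.

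The site gap is a separate matter. With two candidate sites and neither named as the endpoint, hand, face or both could be presented as the TEWL or pH result after the data are known. Eligible irritation may be on the hands, the face or both, so the choice of site also decides which subjects are measured where they have symptoms.

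**Working it through.** **1. The plan's own figure.** The synopsis gives power 0.80 for n = 50, d = 0.4, two-tailed alpha 0.05. A paired t-test with 49 degrees of freedom and noncentrality 0.4 × √50 = 2.83 has power 0.792; the normal approximation gives 0.807. The figure reproduces. It does not bear on this point, which concerns what the endpoint measures.

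**2. Is time since application set or recorded?** The places where it could appear:

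| Place | Content | Application time? |
|---|---|---|
| Section 11.1 and Appendix II footnote | no washing for 2 hours | no |
| Section 11.2 | apply at home to clean skin | no interval before a reading |
| Section 7 | apply after bathing | no interval before a reading |
| Section 11.3 | adverse events, changes to skin routine | no |
| Section 16.5 | product dispensed and returned, other logs | no |
| Appendix II | product collected at Day 28 | no |
| Appendix III | daily counts of hand washing and sanitizer use | no |
| Sponsor manual | not supplied | unknown |

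The visible text is silent. The documents give no size for any on-skin effect, so none is computed.

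**3. Which site is the endpoint?**

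| Place | TEWL | pH |
|---|---|---|
| Synopsis and Section 3, Visits 2 and 3 | dominant hand | dominant hand |
| Sections 11.2 and 11.3 | not stated | face and hand |
| Appendix II | face and hand | face and hand |
| Sections 5 and 21 | not stated | not stated |

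These cannot all be followed. Within the hand, Visit 2 uses the web between the third and fourth metacarpophalangeal joints, while Visit 3 refers to the dorsum of the third and fourth metacarpal phalanges, although the Visit 3 text also requires the same location as Visit 2.

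**4. What would a free choice of site allow?** Assume two-sided alpha 0.05 for secondary outcomes (Section 21 states it only for the primary ones), no true change at either site, and a reduction reported if either site shows one.

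- One named site: 0.05 / 2 = 0.025.
- Two independent sites: 1 − (1 − 0.025)² = 0.0494.
- Two correlated sites: 0.025 + 0.025 − P(both significant), using a bivariate normal. At correlation 0.5 this gives 0.045, and at 0.8 it gives 0.039.
- Perfectly correlated sites: 0.025.

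The between-site correlation is not in the documents; 0 to 1 is the full range for non-negative values.

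**The case against.** **The manual may already set the timing.** This stands. The protocol delegates measurement steps to it, so the finding is silence in the visible text. A reader might infer that timing is uncontrolled at the sites; the documents do not show that. A manual rule would still leave Sections 5 and 21 without a site.

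**The mechanism is not documented.** Section 14.11 mentions the occlusives only in connection with systemic uptake. It says nothing about TEWL readings or how long a film lasts. A reader might infer that a Day 28 reduction would be an artefact; the text supports only that it may include a product effect of unknown size. For pH even the presence of an effect is uncertain.

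**Application just before the reading is unlikely.** Home application to clean skin, with no washing for 2 hours beforehand, does make it less likely. These instructions still set no interval.

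**An on-product reading can be a valid target.** Hypothesis b is that "EpiCeram will improve measurements of skin barrier integrity", and a reading during use can serve that. The plan does not say it is the intended target.

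**The hand is the only site with a stated measurement point.** True, and it is the more natural reading of Section 3. Appendix II nevertheless schedules the face for TEWL and pH, and Sections 11.2 and 11.3 do so for pH.

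**The error-rate figure presumes selective reporting.** It does, and nothing in the documents indicates such an intention. A reader might also quote the two-sided chance of 1 − 0.95² = 9.75%. That includes significant increases, which Section 5 does not count as success. The plan's four-decimal p-values permit later adjustment but do not fix the site.

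**Conclusion.** The point holds as a cheap improvement to two secondary endpoints; the primary symptom analysis, sample size and power are unaffected.

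On timing, the protocol controls product use before baseline and, in its visible text, neither sets nor records time since application at Day 28. A TEWL reduction may therefore include an on-skin product effect of undocumented size, subject to what the manual says.

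On site, the conflict between Section 3, Sections 11.2/11.3 and Appendix II is plain from the text. If either site could be reported, the chance of a false reduction per endpoint rises from 2.5% to between 2.5% and about 4.9%, under the assumed alpha and non-negative correlation.

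A reader might infer that fixing the timing would make the change attributable to EpiCeram. It would not, because the study has no control arm; it removes one avoidable ambiguity.

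Two smaller points remain. The hand-site wording differs between visits. Section 11.1 also allows that "Screening and Baseline procedures may occur on the same day the study is first presented", without saying how the no-wash rule is then met.

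**What to change.** 1. Without prescribing any change to the application regimen, schedule Visit 3 skin-function readings at a standardised point relative to the subject's last application, set by the sponsor, or cite the manual section that already does this.
2. Record time of last application, and time of last wash, on the tablet, and report them with the TEWL and pH results. State how the no-wash condition is met when Screening and Baseline fall on one day.
3. If an on-product reading is intended, state that as the target.
4. Reconcile Section 3, Sections 11.2/11.3 and Appendix II on hand versus face. Name in Sections 5 and 21, before the data are seen, the site that defines each endpoint.
5. Use one hand-site wording at both visits in the synopsis and Section 3. The application intervals in Sections 3 and 7 must also be reconciled.

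The cost is wording changes, one or two extra data fields and slightly less flexible Visit 3 scheduling.
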